To assess the durability of responses, patients who achieved 50% regrowth from baseline (a 50% reduction in baseline SALT score) during the first 6 months, will continue to be followed for an additional 6 months off treatment or until it is determined that relapse has occurred. Percent hair regrowth from baseline will be determined by SALT measurements during the observational phase at weeks 28, 32, 36, 40, 44 and 48. Relapse will be defined as any recurrence of hair loss in responders (subjects achieving greater than 50% decrease in SALT score from baseline during the first 6 months of the study) who had achieved stable regrowth without continued loss for at least 2 months; and loss of $\geq 25\%$ of regrowth in patients who had achieved 50% regrowth but still had chronic low grade hair loss.

Nonresponders to 6 months study treatment (defined as failure to achieve 50% improvement in SALT score at week 24 compared to baseline) will not be required to participate in the 6mth follow-up period but will be given the option of receiving monthly IL TAC 2.5mg/ml, 5mg/ml or 10mg/ml injections for 6 months if deemed appropriate by the investigator. The dosage to be utilized (2.5mg/ml vs. 5mg/ml vs. 10mg/ml) will be based on clinical considerations, unless study data is available to support preference of one dose versus the

other. Patients identified by unblinded study personnel as having previously been treated with active drug or with obvious signs of atrophy or other indications suggesting they have already been treated with active drug for 6 months will not be given the option of continuing IL TAC as it is unlikely that they will respond if they have not responded by 6 months unless available evidence suggests that utilization of a different dosage is more likely to be efficacious and safe.

Human Subjects Involvement, Characteristics, and Design

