As secondary endpoints, efficacy will be measured by changes in hair re-growth as a continuous variable as determined by physical exam and Canfield photography, as well as patient and physician global evaluation scores. To assess the durability of responses, patients who achieve 50% reduction in baseline SALT score will continue to be followed for an additional 6 months off treatment.

Secondary efficacy outcomes will include:

1. Percent hair regrowth from baseline determined by SALT measurements following 12, 24 weeks of treatment and at weeks 36 and 48 following discontinuation of treatment (Price et al Efalizumab study)
2. Comparison of the proportion of responders in each group, with response defined as 50% change in SALT score (50% regrowth) from baseline, at weeks 12, 36 and 48.
3. Comparison of the proportion of subjects in each group attaining global overall improvement SALT score of A5 (100% coverage) supported by </= SALT 25 at weeks 12, 24, 36 and 48.
4. Change in PGA (Physician global assessment) based on evaluation of live evaluations and standardized photographs between baseline, week 12, 24, 36 and 48
5. Change in patient global assessment (100mm Visual analogue scale) between baseline, Week 12, 24, 36 and 48
6. Change in patient quality of life assessment (DLQI or DQLS) from baseline to weeks 12, 24, 36 and 48. (Finlay and Khan 1994).
7. Frequency of occurrence and timing of relapse (as defined above) in responders followed for 6 months off therapy.

Safety and tolerability measures:

Incidence and severity of adverse effects (AEs) including the presence and degree of skin atrophy.

Incidence of treatment-emergent laboratory abnormalities.

Sample size

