Power analysis is based on a chi-squared test of proportions of responders in the 4 study groups, where response is defined as 50% reduction in SALT score. Effect size is quantified in terms of Cohen's w , a function of the response rates in the fourgroups (15). A minimal treatment effect size of 40% (Cohen's $w = 0.4$) i.e. a 50% response rate for active drug (IL TAC 2.5mg/ml, 5mg/ml or 10mg/ml) versus a presumed spontaneous remission response rate of 10% for patients receiving inactive IL saline, would be considered clinically meaningful in this study. To achieve 80% power to detect the desired effect size of 40% with a usual 5% level of significance (alpha), we would require approximately 17 subjects per arm (68 subjects in total). With this sample size, an effect size of 50% (Cohen's $w = 0.5$, "large" effect) would ensure approximately 95% power. Our postulated effect size for IL TAC is based on impressions due to clinical use of IL TAC in AA, however an explicit aim of this pilot study is to objectively and more precisely quantify the actual treatment effect of the various doses of IL TAC versus saline placebo.

Data Analysis Plan

The primary analysis will be a comparison of response rates in the 4 study groups, using a chi-squared test of proportions. If the 4-group comparison is significant, we will compare the efficacy and safety profiles of the three doses of intralesional triamcinolone head to head. For secondary outcomes that are binary (response/non-response), we will follow the same strategy. For secondary outcomes that are continuous (e.g. change in SALT measurement or PGA), we will conduct 4-group ANOVA tests, followed by pairwise

comparisons, if necessary. In both cases, Bonferroni correction will be made to adjust for multiple testing. To assess safety, we will summarize and test the incidence rates of adverse events across groups.

If possible, we will attempt to stratify the patients based on baseline degree of hair loss e.g. 0-25% vs. 26-50% hair loss in order to assess if response is correlated with degree of hair loss present at baseline. (Olsen E. Investigative guidelines for alopecia areata.

Dermatologic therapy 24, 2011 311-319

All outcomes will be analyzed on the intent to treat (ITT) basis.

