A 3-month interim analysis of the primary and secondary outcomes will be performed by an independent group in order to determine if statistical significance has been attained. A Haybittle-Peto rule for alpha spending (Haybittle 1971; Peto et al. 1976) will be followed for the interim analysis. If statistical evidence of efficacy is attained at 3 months and if the safety profile is acceptable, all patients will be offered the option of receiving open label active drug for the remaining duration of the trial.

To compare the frequency of occurrence of relapse in responders (followed for 6 months off therapy) across the four groups, we will employ a chi-squared test for comparing multiple proportions.

Furthermore, to compare the timing of relapse in responders (followed for 6 months off therapy) across the four groups, we will use tools from survival analysis (or, time-to-event analysis, with relapse as the event of interest). More specifically, first, we will conduct a descriptive analysis by graphically comparing the Kaplan-Meier survival (time-to-relapse) curves for the four groups. Next, we will use the log-rank test to formally test the null hypothesis of no difference between the survival functions of the four groups.

Specific Aim 2. To identify a clinical correlation between treatment outcome and down modulation of key AA-associated immunohistopathological markers and biomarkers in the treated skin; including NKG2DL expression in the hair follicle, immune infiltration (CD8⁺NKG2D⁺ cells) and expression of interferon response genes.

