An unblinded member of the study team who is not involved in patient assessment will examine the efficacy and safety data available when all subjects have completed 3 months of study drug. Efficacy and safety parameters will be put in place to determine if efficacy has been established at this time point. If efficacy has been established and the safety profile is acceptable, study participants will be offered the option to continue the study in an open label format for the remaining duration of the study.

Regulatory Considerations

Institutional Review Board/Independent Ethics Committee Review and Approval

The protocol for this study has been designed in accordance with the general ethical principles outlined in the Declaration of Helsinki. The review of this protocol by the IRB/IEC and the performance of all aspects of the study, including the methods used for obtaining informed consent, must also be in accordance with principles enunciated in the declaration, as well as ICH Guidelines, applicable local health authority regulations, and US Title 21 of the Code of Federal Regulations (CFR), Part 50 Protection of Human Subjects and Part 56 Institutional Review Boards. Before implementing this study, the protocol, the proposed informed consent form and other information to subjects, must be reviewed by a properly constituted IRB/IEC.

The investigator(s) will be responsible for preparing documents for submission to the relevant IRB/IEC and obtaining written approval for this study. The approval will be obtained prior to the initiation of the study. The investigator is responsible for notifying the IRB/IEC of any serious deviations from the protocol, or anything else that may involve added risk to subjects.

Informed Consent

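### If the month-3 interim crosses, responders may restart drug during off-treatment follow-up, and the relapse analyses have no censoring rule, so off-drug relapse would be misestimated

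*Combined protocol and SAP*

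**What the plan says.** The offer appears twice. In the Data Analysis Plan, if efficacy is shown at 3 months and safety is acceptable, "all patients will be offered the option of receiving open label active drug for the remaining duration of the trial". In the Data and Safety Monitoring Plan, "study participants will be offered the option to continue the study in an open label format for the remaining duration of the study", and the data are examined "when all subjects have completed 3 months of study drug". This is therefore a single calendar look, taken after the last subject enrolled has reached month 3.

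Durability is part of Specific Aim 1. Responders "will continue to be followed for an additional 6 months off treatment or until it is determined that relapse has occurred" (METHODS, Specific Aim 1). The matching secondary outcome, item 7 under Study outcomes, is "Frequency of occurrence and timing of relapse (as defined above) in responders followed for 6 months off therapy".

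The Data Analysis Plan uses a chi-squared test "To compare the frequency of occurrence of relapse in responders (followed for 6 months off therapy) across the four groups". It uses Kaplan-Meier curves and a log-rank test "to compare the timing of relapse in responders (followed for 6 months off therapy) across the four groups". The only general rule for data after a change of treatment is "All outcomes will be analyzed on the intent to treat (ITT) basis". No sentence says whether a responder who takes open-label drug before relapsing is censored, excluded or kept.

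**The concern.** Because the look waits for the last subject's month 3, earlier enrollees will be spread over the 48-week course by then. Some responders will be in weeks 24-48 off drug and others will be approaching week 24. The offer covers both groups.

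A responder who restarts drug can no longer show relapse off drug. If that responder stays in the denominator as relapse-free, off-drug relapse is understated. If the phrase about six months off therapy is used to drop that responder, the loss is selective: follow-up ends at relapse, so only responders who have not relapsed can be dropped, and relapse is overstated. Durability after stopping drug, which the trial sets out to measure, would then depend on a choice made after the interim result is known.

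**Working it through.** **The plan's own figures.** It gives none for relapse. Its power figures reproduce: noncentral chi-squared, 3 df, noncentrality N·w². At N = 68, w = 0.4: 68 × 0.16 = 10.88, power 79.9% (stated 80%). At w = 0.5: 68 × 0.25 = 17, power 94.8% (stated about 95%).

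**Chance that the problem arises.** The plan names a Haybittle-Peto rule without a threshold, so p < 0.001 is my assumption. Simulating the four-group chi-squared test with 17 per arm gives 5.7% at 40/40/40/5, about 14% at 50/50/50/10 and about 42% at 60/60/60/10. The plan postulates 50% versus 10% for week 24; a smaller effect at month 3 would lower the chance.

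**Inputs for relapse.**
- Accrual of T = 52 or 104 weeks, taken as uniform. Recruitment gives a 1 to 2 year study period; the uniform shape is assumed.
- Interim at calendar week T + 12, with no analysis lag (assumed).
- Off-drug phase from week 24 to week 48, or until relapse.
- True 24-week relapse risk p with constant hazard, full uptake and no relapse on drug (all assumed).

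**Position of responders at the interim.**
- Not yet at week 24: P = 12/T = 23.1% / 11.5%
- In weeks 24-48: F = 24/T = 46.2% / 23.1%
- Finished: C = (T − 36)/T = 30.8% / 65.4%

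The mean relapse risk already accrued by those in weeks 24-48 is a = 1 − p/(−ln(1 − p)). At p = 0.5, a = 1 − 0.5/0.693 = 0.279.

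**Formulas.** Observed relapses per responder are x = C·p + F·a. At p = 0.5:
- T = 52: 0.308 × 0.5 + 0.462 × 0.279 = 0.282
- T = 104: 0.654 × 0.5 + 0.231 × 0.279 = 0.391

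Kept in, all responders: x. Kept in, only those past week 24 at the interim: x/(C + F). Restarters dropped: x/(C + F·a).

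| True relapse | Kept in, all (52 / 104 wk) | Kept in, past week 24 | Restarters dropped |
|---|---|---|---|
| 30% | 16.6% / 23.3% | 21.5% / 26.3% | 43.5% / 33.7% |
| 50% | 28.2% / 39.1% | 36.7% / 44.2% | 64.7% / 54.5% |
| 70% | 40.9% / 55.4% | 53.1% / 62.7% | 81.6% / 73.9% |

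The all-responder column is the relevant one for keeping restarters in, because responders not yet at week 24 get the same offer.

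**Milder assumptions, true 50%, all responders kept in.** Half uptake: 0.5 − 0.5 × (0.5 − x) = 39.1% / 44.6%. Full uptake with the relapse hazard halved on drug: 40.8% / 45.4% (simulated).

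**With censoring at the first open-label injection.** Simulated Kaplan-Meier at 24 weeks off drug returns 50% for a true 50%, and 30% for a true 30%, at both accrual lengths, when uptake is unrelated to prognosis.

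**Precision.** Expected responders: 51 × 0.5 + 17 × 0.1 = 27.2. The standard error of a 50% proportion is √(0.25/27.2) = 9.6 points. The kept-in bias is 11-22 points at full uptake and 5-11 at half uptake.

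**Week-24 comparison.** The last scheduled injection before week 24 is at week 20 (Study procedures), so the exposed share is 8/T = 15.4% / 7.7%. The placebo rate becomes 0.10 + (8/T)(r − 0.10), where r is the assumed response of a switched placebo subject:
- r = 0.25: 12.3% / 11.2%
- r = 0.50: 16.2% / 13.1%
- T = 26, exposed share 30.8%: 14.6% or 22.3%

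**The case against.** **The offer does not reach responders.** The visit list for weeks 28-48 and the Schedule of Assessments give open-label drug after week 24 only to qualifying nonresponders. That is the path when the interim does not cross. The two interim statements are separate and carry no such limit. If responders were meant to be excluded, one sentence would settle it.

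**Censoring is the natural reading.** The target is relapse off therapy, and Kaplan-Meier methods handle censoring, so an analyst might well end follow-up at restart. This is fair for the time-to-relapse analysis. It does not rescue the chi-squared test on raw proportions, which has no place for a partly followed responder, and the only written rule is intent to treat.

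**The accrual range is too slow.** Recruitment says the 1 to 2 year period also allows for treatment and follow-up. If it must contain the 48-week course, accrual is at most about 56 weeks (104 − 48). The formulas at T = 56 give 29.8% kept in and 62.5% with restarters dropped, so the larger relapse bias applies. Faster accrual also raises the week-24 dilution, and with accrual of 12 weeks or less nobody would be in relapse follow-up at the look. This objection stands: no accrual speed is documented.

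**The planned test is a group comparison.** The offer goes to every arm, and the figures here are pooled rates. No effect on the error rate or power of the four-group relapse tests has been shown. With about 27 responders, fewer than 2 expected on placebo (17 × 0.1), those tests carry little information anyway. A reader might infer that they are invalid; nothing here establishes that.

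**Conclusion.** The point holds as a minor one. If the interim crosses, following the written rules gives the wrong off-drug relapse rate: a true 50% reads as about 28-39% with restarters kept in, or about 54-65% with them dropped. These figures rest on uniform accrual over 52-104 weeks, full uptake, no relapse on drug, constant hazard and no analysis lag. Half uptake cuts the kept-in bias by half.

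It is minor because it is conditional on crossing (about 6-14% at 40/5 to 50/10) and because it affects secondary outcomes of a study that calls itself a pilot. The week 36 and 48 secondary outcomes would also mix off-drug and open-label time; I have not sized that.

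Two stronger readings are tempting:
- **The primary comparison is compromised.** The documents do not support this. Exposure before week 24 is limited to subjects who can still have an injection by week 20, and initial regrowth is expected only after 4 to 8 weeks. Nor can the dilution be called slight without qualification, since it grows with faster accrual.
- **Durability will be misestimated whatever happens.** If the interim does not cross, the offer is never made.

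**What to change.** Add to the Data Analysis Plan, before the interim data are seen:

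1. In the relapse analyses, time runs from week 24 and is censored at the first open-label injection. Responders who restart drug stay in the analysis up to that point.
2. Relapse frequency is the censored Kaplan-Meier estimate at 24 weeks off drug, by arm, in place of the raw proportion.
3. Report by arm the number censored for restarting and their SALT at the switch.
4. Add a sensitivity analysis that counts restarting as relapse, because subjects who notice shedding may be the first to accept drug.

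This needs no extra subjects or visits. It has limits. At full uptake the sensitivity bound is wide: 1 − C(1 − p) gives 84.6% / 67.3% for a true 50% at 52 / 104 weeks. A responder who restarts at week 24 contributes no off-drug time. If accrual is fast and uptake complete, nobody reaches 24 weeks off drug: at T = 26 the longest off-drug time at the interim is 26 + 12 − 24 = 14 weeks, and the simulated censored estimate reads 33% for a true 50%. The estimate should then be quoted at the last week with responders still at risk.

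I would not delay the open-label offer until week 24. That would withhold drug for up to 12 weeks after efficacy is declared, and would still let responders restart at week 24 with no off-drug data.

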in which fewer than 10% are expected to achieve this magnitude of hair regrowth spontaneously. In contrast, clinical experience would suggest that approximately 50% of subjects treated with either dose of IL TAC may achieve $\geq 50\%$ improvement in SALT score after 6 months of treatment. The goal of this study is to validate or refute this clinical impression and to objectively and precisely quantify the treatment effect of 2.5mg/ml, 5mg/ml or 10mg/ml of IL TAC in AA.

Subjects will be randomized 1:1:1:1 to the placebo or treatment arms, and will receive 6 months of treatment with the study medication or placebo. IL TAC 2.5mg/ml, 5mg/ml, 10mg/ml or placebo will be administered at baseline, then every 4 weeks thereafter for 5 cycles (weeks 4, 8, 12, 16, 20) for a total treatment period of 6 months. Percent hair regrowth from baseline will be determined by SALT measurements following 4, 8, 12, 20 and 24 weeks of treatment. Punch biopsies and peripheral blood will be obtained at baseline prior to treatment, and then once again at a time point between weeks 4 and 20, to be determined by the investigator as indicated by clinical considerations such as variation in the timeline to regrowth from one subject to another, for immunomonitoring/biomarker studies. Additional, optional scalp biopsies and blood draws may be taken at other key time points in order to monitor response to therapy at the discretion of the investigator and with the consent of the study subject. Efficacy will be measured by change in hair re-growth as determined by physical exam and photography, as well as by patient and physician global evaluation scores. Physician and patient global evaluation scores will be determined based on the use of similar 100mm Visual Analogue scales with 0 labeled as no scalp hair loss and 100 labeled as complete scalp hair loss. Patients and physicians will place a vertical mark along the horizontal line depending on their assessment of the degree of hair loss present at the time of assessment.

As secondary endpoints, efficacy will be measured by changes in hair re-growth as a continuous variable as determined by physical exam, SALT score and Canfield photography, as well as patient and physician global evaluation scores.

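### Relapse is formally tested across four arms in responders only, where about 1.7 placebo responders are expected; the listed week-36 and week-48 responder comparison has no rule for week-24 non-responders

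*Combined protocol and SAP*

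**What the plan says.** - **Relapse tests.** The Data Analysis Plan introduces a chi-squared test with the words "To compare the frequency of occurrence of relapse in responders (followed for 6 months off therapy) across the four groups". For timing it plans Kaplan-Meier curves as a descriptive step and then says "we will use the log-rank test to formally test the null hypothesis of no difference between the survival functions of the four groups".
- **Population.** The same section states: "All outcomes will be analyzed on the intent to treat (ITT) basis". Under METHODS, Specific Aim 1, relapse is defined only for subjects who have responded.
- **Expected response.** Sample size assumes 10% response on saline and 50% on each of the three doses, with 17 subjects per arm. METHODS describes the saline arm as one "in which fewer than 10% are expected to achieve this magnitude of hair regrowth spontaneously".
- **Follow-up after week 24.** METHODS and Study procedures (Baseline to Week 48) keep responders under observation off treatment to week 48 or until relapse. Non-responders at week 24 need not be followed. They may be offered six months of open-label IL TAC, an option generally withheld, with an exception, from those known or suspected to have had active drug.
- **Later responder comparison.** Both lists of secondary outcomes (Assessment of efficacy; Study outcomes) include the proportion of responders in each group at weeks 36 and 48. The Data Analysis Plan gives binary secondary outcomes the same four-group strategy as the primary outcome.

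The plan states no relapse rate, event count or power for the relapse comparison. It gives no caveat about selection on response, and no rule for classifying week-24 non-responders at weeks 36 and 48.

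**The concern.** Durability off treatment is part of Specific Aim 1, and the plan commits to two formal tests of it. Both are confined to a subset formed after randomisation by an outcome the drug is expected to change fivefold. Placebo responders would be spontaneous remitters. Under the planning rates, most responders on active drug would owe their response to the drug. A difference in relapse could therefore reflect who responded rather than what the drug did. With one or two placebo responders, a non-significant four-group p-value could also be misread as evidence of equal durability.

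The week-36 and week-48 responder comparison could use the randomised denominator, but it has its own gap. A placebo subject who fails at week 24 and then regrows hair on open-label IL TAC could be counted as a placebo responder at week 48.

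**Working it through.** **1. The plan's own figure.** Four-group chi-squared test, df = 3, alpha 0.05, noncentrality N × w². At N = 68 and w = 0.4 this is 68 × 0.16 = 10.88, and power is 79.9%. At w = 0.5 it is 68 × 0.25 = 17, and power is 94.8%. The stated 80% and approximately 95% are reproduced, so 17 per arm is used below. (Whether 10/50/50/50% corresponds to w = 0.4 is a separate matter and does not enter here.)

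**2. Expected responders.** Placebo: 17 × 0.10 = 1.7. Each dose: 17 × 0.50 = 8.5. Total: 1.7 + 3 × 8.5 = 27.2.

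**3. Chance of very few placebo responders, Binomial(17, p).** At p = 0.10, P(0) = 0.9^17 = 0.167, and P(1) = 17 × 0.1 × 0.9^16 = 0.315. The range uses the 7% saline regrowth and the 20% spontaneous recovery reported under Clinical experience with IL TAC for AA.

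| Placebo response | Expected responders | P(0) | P(at most 1) | P(at most 2) |
|---|---|---|---|---|
| 7% | 1.2 | 29% | 66% | 89% |
| 10% (planning value) | 1.7 | 17% | 48% | 76% |
| 20% | 3.4 | 2% | 12% | 31% |

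At 10%, about one trial in six would have no placebo group in the four-group relapse test. Since METHODS expects fewer than 10%, 1.7 is at the upper end of the plan's own expectation.

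**4. Rejection rate of the four-group chi-squared test in responders.** By simulation: responders drawn as Binomial(17; 0.1, 0.5, 0.5, 0.5), relapse drawn among them, Pearson test at 5%. All relapse rates are assumptions.

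| Relapse, placebo / three doses | Rejection rate |
|---|---|
| 50 / 50, 50, 50% | 4% |
| 70 / 30, 30, 30% | 11% |
| 90 / 30, 30, 30% | 18% |
| 50 / 70, 50, 30% | 25% |
| 50 / 80, 50, 20% | 56–57% |

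The size is acceptable, so the difficulty is the subset and not the chi-squared approximation. With placebo response at 20%, the 11% and 18% become 19% and 38%. Among the three doses alone, the last two rows give about 30% and 63%.

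**5. Log-rank.** For a simplified contrast of placebo with pooled active, the placebo share is 1.7/27.2 = 1/16. With an assumed hazard ratio of 0.5, the Schoenfeld formula requires (1.96 + 0.84)² / [(1/16)(15/16)(ln 0.5)²] ≈ 279 events. At most about 27 are available. Power is 9% if half the responders relapse and 14% if all do. The formula is rough at such counts, but the order of magnitude is clear.

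**6. Open-label carry-over at week 48.** Expected placebo non-responders at week 24: 17 × 0.90 = 15.3. As an illustration, suppose a fraction u takes open-label drug and responds at the plan's 50% rate, with no relapse among the spontaneous responders. Apparent placebo response is then 0.10 + 0.90 × 0.50 × u: 32.5% at u = 0.5 and 55% at u = 1. Uptake is not given in the plan; the point is that the rule matters.

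**7. What a sustained-response endpoint measures.** Count as a success, among all 68, a week-24 response without later relapse. With relapse equal at 30% in every arm, the success rates are 0.10 × 0.70 = 7% and 0.50 × 0.70 = 35%. The four-group test then rejects about 45% of the time although durability does not differ.

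**The case against.** Relapse is a secondary outcome in a self-described pilot, no power is claimed for it, and the curves are already presented descriptively first. Relapse has no meaning without prior response, and the plan openly labels the outcome as confined to responders, so nobody is misled about the denominator. All of this stands. It limits the point to interpretation of a secondary outcome, and it makes the ITT sentence over-general rather than a hidden contradiction. It does not rescue two formal four-group tests in a non-randomised subset.

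Three stronger readings are tempting, and the documents do not support them.

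- *A reader might infer that the plan has no randomised comparison bearing on durability.* It lists responder proportions by group at weeks 36 and 48. What is missing is the rule for non-responders and relapsers.
- *A reader might infer that the relapse analysis holds almost no information anywhere.* That is fair for contrasts with placebo. Between doses, with about 8.5 responders each, power is low but not negligible if the doses differ widely (25% to 57% in the four-group test).
- *A reader might infer that a sustained-response endpoint is simply a more powerful test of durability.* It is not. It mixes response with relapse and rejects about 45% of the time with equal relapse, because of the response difference alone. The two tests address different hypotheses, so their power should not be compared.

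**Conclusion.** The point holds as a cheap improvement to a secondary analysis. The four-group relapse tests condition on a post-randomisation outcome, and any contrast with placebo rests on an expected 1.7 subjects (17% chance of none, 48% of at most one). Power is about 11% or 18% under assumed relapse of 30% on each dose and 70% or 90% on placebo. These figures rest on the plan's response rates and 17 per arm with no dropout; dropout would lower the counts. The relapse rates are assumptions. METHODS selects subjects for follow-up on regrowth at any time in the first six months but judges non-response at week 24, so the numbers actually followed may differ somewhat from 1.7 and 8.5.

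The listed week-36 and week-48 responder comparison is the natural randomised complement, but as written it could credit open-label regrowth to placebo. The primary analysis is not affected.

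**What to change.** 1. For the week-36 and week-48 responder comparison, specify all randomised subjects as the denominator and count week-24 non-responders and subjects who have relapsed by that week as failures, whatever open-label treatment follows. Call it sustained response, and say that it combines response and durability and does not isolate durability.
2. Present relapse among responders by arm descriptively, with counts and Kaplan-Meier curves, and make no formal contrast with placebo. Label any test among the three active doses exploratory, because it too is conditional on response.
3. State that the relapse outcome is an exception to the ITT sentence.

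Cost: SAP wording only, using assessments already scheduled to week 48. The downside is that sustained response mixes two things, which is why the responder-only curves stay beside it.
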